4.5.1 Other Adverse Events

All adverse events will be summarized through 12 months. The proportions of subjects with events will be reported. No imputation for missing data is planned.

Tabular summaries by treatment group of all adverse events, adverse device effects, serious adverse events, and serious adverse device effects will be presented.

An adverse event (AE) is defined as any untoward medical occurrence, unintended disease or injury or untoward clinical signs (including an abnormal laboratory finding) in subjects,

users or other persons, whether or not related to the investigational medical device. An Adverse Device Effect (ADE) is defined as an adverse event related to the use of an investigational medical device. A serious adverse event (SAE) is an adverse event that:

- a) led to a death
- b) led to a serious deterioration in the health of the subject, that either resulted in: a life-threatening illness or injury, or a permanent impairment of a body structure or a body function, or in-patient or prolonged hospitalization, or -medical or surgical intervention to prevent life threatening illness or injury or permanent impairment to a body structure or a body function.
- c) led to fetal distress, fetal death or a congenital abnormality or birth defect. A serious adverse device effect (SADE) is an adverse device effect that has resulted in any of the consequences characteristic of a serious adverse event.

The investigator will assess each adverse event for its relationship to the study device, and whether it was anticipated in the protocol. The determination of the relationship between the adverse event and the device is made according to the following definitions:

- Definitely related (causal relationship)
- Probably related
- Possibly related
- Not related
- Unknown.

Acute peri-procedural complications (related to the study procedure and occurring within one week of the ablation procedure), will be specifically analyzed as part of the exploratory endpoints.

5 Assessing the Primary Outcome

Freedom from documented AF between 3 and 12 months following the index ablation procedure will be defined as no documented episodes of AF > 30 seconds with conventional non-invasive monitoring.

The following scenarios result in primary endpoint failure:

- 1) A repeat procedure where AF is confirmed during the procedure (Patient is in spontaneous AF at the beginning of the procedure)
- 2) A 30-second or greater episode of AF is documented on a 24-hour Holter

- 3) A 30-second of AF on a weekly TTM transmission confirmed by 30-second of AF on same (but different day) or next week TTM transmission. Two AF transmissions on the same day do not count as a confirmed recurrence.
- 4) Since 12-Lead ECGs are 10 seconds in duration, an AF episode of >30 seconds will be documented via 12-lead EGC under only certain conditions (AF symptoms, multiple ECGs recorded at a single visit showing AF, confirmation of single Kardia in AF in same, previous or next week).

TTM will be measured weekly by the patient via a portable ECG device (KardiaMobile, AliveCor). The recordings will be automatically uploaded for blind review by the ECG core lab.

24-hour Holter monitor assessments will be performed prior to or subsequent to each inoffice visit at 3, 6, and 12 months post-index procedure.

Diagnostic 12-lead ECGs will be performed at each in-office visit at 3, 6, and 12 months following the index procedure.

6 General Statistical Considerations

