## IV – ENDPOINTS OF THE CLINICAL INVESTIGATION

### 4.1 – Primary endpoint

The primary endpoint is defined in Table 2.

Table 2: Primary endpoint

Endpoint	Description
Long-term effectiveness primary endpoint	
1. Freedom from documented AF*, with or without AADs, 12 months after a single index ablation procedure.
 
*Freedom from documented AF is defined as no documented episodes of AF > 30 seconds with conventional non-invasive monitoring (Holters, TTM and 12-lead ECG recordings) between 3 and 12 months after index procedure
 
Difference of freedom from arrhythmia between the arms will be analyzed as comparison of survival distributions of the two arms in order to take into account the time to arrhythmia recurrence and the censored data (cf. 6.5 – Evaluation criteria for primary and secondary endpoints)

Possible scenarios that may result in primary endpoint failure:

- A repeat procedure where AF is confirmed during the procedure
- A 30-second or greater episode of AF is documented on a 24-hour Holter prior or subsequent to a follow-up visit
- 30-second of AF on a weekly TTM transmission confirmed by 30-second of AF on same or next week TTM transmission
- A 10-second 12-lead ECG recording confirming AF suggested by either TTM or Holter and subject symptoms

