## **V – DESIGN OF THE STUDY**

### **5.1 – General**

#### 5.1.1 – Description of the type of clinical investigation

This study concerns a medical device post-CE marking, and has the following characteristics:

- Interventional: Enrolled patients will undergo an AF ablation
- Prospective: Patients are enrolled prior to undergoing an AF ablation
- Multi-center: This study will take place in several sites, at least 5 different sites with a maximum number of inclusions per site as defined in this protocol (cf. 6.8 – Minimum and maximum number of subjects to be included for each site). A maximum of 8 sites may participate in the United States.
- Controlled: Patients in the Anatomical arm (conventional procedure) constitute the control group
- Randomized, two-arm: At enrollment, the patient is randomized 1:1 to one of the arms, Anatomical or Tailored
- Simple-blinded: The patient is not aware of the randomization

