#### 5.1.2 – Description of measures to be taken to minimize or avoid bias

All patients will be randomized at enrollment in a 1:1 ratio. The patient will not be informed of the randomization.

Special care will be taken to ensure that the patient will be blinded to his/her randomization assignment throughout the study. Patient unblinding should be documented as a non-important deviation.

Moreover, a blind rhythm monitoring is planned: all ECG recordings for long-term effectiveness endpoints (Holter, TTM and 12-lead ECG) will be analyzed and adjudicated blindly by an independent ECG core lab.

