#### Re-ablation procedure in Tailored group

In the Tailored group, a re-ablation procedure will be performed using the same approach as the first index procedure. The redo procedure endpoint is also *sinus rhythm conversion by ablation* at dispersion regions and potential subsequent AT. In addition, a CTI anatomical line is allowed.

If the repeat procedure is performed for an AT recurrence, AF induction is not required at the beginning of the procedure.

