#### Re-ablation procedure in Anatomical group

During a repeat ablation in the Anatomical group, PV reconnections will be checked, and potentially reconnected PV will be re-isolated.

A maximum of two additional anatomical lines are allowed (0, 1 or 2 lines): roof and/or mitral isthmus and/or CTI lines or posterior box isolation (no other lines are allowed).

The redo procedure endpoint is *isolation of all four PVs and lines validation*.

In case of regularization into AT during anatomical re-ablation, mapping (without VX1) and ablation of the AT is allowed. If the repeat procedure is performed for an AT, it can be mapped (without VX1) and ablated.

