### 5.3.9 – Visit schedule

Study visits that do not occur within time windows in Table 8 will be considered protocol deviations.

Table 8: Time windows for study visits

Visit	Screening, enrollment, and randomization	Index procedure	3-month follow-up	Redo procedure (if required)	6-month follow-up	12-month follow-up
Timing	Prior to index procedure	0 – 90 days after enrollment	2M + 1 day to 3M after index procedure	3M to 9M after index procedure	6M ± 30 days after index procedure	12M ± 30 days after index procedure

5.3.10 – Summary of required clinical assessment and data collection

Table 9 summarizes study visits and required assessments and data collection.

*Table 9: Schedule of events*

Event	Screening	Enrollment	Index procedure	3-month follow-up visit	Redo procedure (if required)	6-month follow-up visit	12-month follow-up visit	Unscheduled follow-up visit
Inclusion and exclusion criteria assessment	X							
Informed consent	X							
Demographics, medical history, cardiac diagnosis		X						
Documentation of AF (ECG, physician's letter)		X						
12-lead ECG		X		X		X	X	X
Physical exam		X		X		X	X	X
Concomitant cardiac medications		X	X	X	X	X	X	X
AF assessment (AF presence and/or AF recurrence since last follow-up)		X	X	X	X	X	X	X
QoL questionnaire		X		X		X	X	
24h ambulatory continuous ECG (Holter)				X		X	X	
Adverse Events review		X	X	X	X	X	X	X
AF interventional procedure			X		X			

 <small>ARTIFICIAL INTELLIGENCE SERVING HEART DISEASE</small>	CLIPL-01-002-E	CONFIDENTIAL
	CLINICAL INVESTIGATION PLAN	F 09 XX 01 Rev.A

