6.9 CORRECTION FOR MULTIPLE-TESTING

For the two secondary efficacy endpoints, the same variable will be observed after up to two procedures (one or two procedures), or after a single procedure. Given the potential number of patients receiving a second ablation procedure (between 22% and 33%¹), the variable for both secondary efficacy endpoints will be the same for most patients, meaning that the two variables will be highly correlated. The third secondary endpoint relates to safety, and is therefore of a different nature. Consequently, no correction for multiple testing will be applied for secondary endpoints.

7 Changes from protocol

Primary endpoint hypothesis in the protocol was wrongly based on the effect size observed in a previous study and used in the sample size estimation (delta 15%, HR = 0.547). The study is powered to detect such an effect size. The tested hypotheses were corrected to H0: S1(t) = S2(t) and HA: S1(t) > S2(t).

The gatekeeping approach for secondary endpoints was abandoned. There are 3 secondary endpoints of different nature (2 highly-correlated efficacy, 1 safety) and therefore no multiple-testing correction will be applied.

8 References

- 1. Verma, A. et al. "Approaches to catheter ablation for persistent atrial fibrillation." New England Journal of Medicine 372 (2015): 1812–1822.
- 2. Fink, T. et al. "Stand-alone pulmonary vein isolation versus pulmonary vein isolation with additional substrate modification as index ablation procedures in patients with persistent and long-standing persistent atrial fibrillation: the randomized alster-lost-AF Trial (ablation at St. Georg hospital for long-standing persistent atrial fibrillation)." Circ Arrhythm Electrophysiol 10, (2017).
- Mehta, Cyrus R., and Stuart J. Pocock. "Adaptive increase in sample size when interim results are promising: a practical guide with examples." Statistics in medicine 30.28 (2011): 3267-3284.

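### Primary-endpoint failure through spontaneous AF at the start of a redo lies outside the stated scope of the blinded ECG core lab, and no assessor is named for it

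*SAP*

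**What the plan says.** Protocol 4.1 gives the route as "A repeat procedure where AF is confirmed during the procedure". SAP section 5, which prevails over the protocol where they differ, narrows it to "A repeat procedure where AF is confirmed during the procedure (Patient is in spontaneous AF at the beginning of the procedure". Neither text names a reader, a type of recording or a minimum duration for this route.

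On blinded review, protocol 5.1.2 states that "all ECG recordings for long-term effectiveness endpoints (Holter, TTM and 12-lead ECG) will be analyzed and adjudicated blindly by an independent ECG core lab"; SAP 6.6 uses the same words. Among those treating the patient and the patient, only the patient is masked: "Simple-blinded: The patient is not aware of the randomization".

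In protocol Table 9 the redo column is marked for the row "AF assessment (AF presence and/or AF recurrence since last follow-up", but not for the 12-lead ECG or Holter rows.

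The redo workflows in protocol 5.3.7 differ by arm. In the Tailored group "a re-ablation procedure will be performed using the same approach as the first index procedure"; in the other group, "During a repeat ablation in the Anatomical group, PV reconnections will be checked, and potentially reconnected PV will be re-isolated".

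Under SAP 6.2, a redo inside the 3-month blanking period with the patient in spontaneous AF counts as a recurrence at 3 months. SAP 4.2 allows redos for non-AF indications without treating them as failures.

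**The concern.** Operators cannot be masked in this trial, so blind reading of rhythm recordings is the main protection for the primary endpoint. Three of the four routes have that protection in writing and the first does not. The person performing a redo follows an arm-specific workflow and therefore knows the arm. Whether the patient arrived in AF, and whether that AF was spontaneous or provoked, decides whether the redo is a failure or a non-AF redo that leaves the patient event-free.

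The route matters most for two kinds of patient. One is the patient whose AF has not yet met the Holter, TTM or ECG rule, for example a single TTM reading that awaits confirmation. The other is the patient re-ablated inside the blanking period: recordings from that period do not count, so at that point the redo rhythm alone decides. If the calls differ by arm, the comparison is biased, and no listed analysis would show it. The named sensitivity analysis for the primary endpoint is the per-protocol repeat (SAP 4.2.4). The others change the AF-duration term (4.2.5) or the subgroup (4.2.6). SAP 6.3 promises supportive analyses, but only for missing data.

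**Working it through.** **Coverage, route by route**

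| Route (SAP 5) | Recording | In core-lab scope (protocol 5.1.2, SAP 6.6) |
|---|---|---|
| 1. Redo with spontaneous AF at the start | none named | not listed |
| 2. Holter | 24-hour Holter | yes |
| 3. TTM, confirmed | TTM | yes |
| 4. 12-lead ECG, with conditions | 12-lead ECG | yes |

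Table 9 schedules no core-lab-type recording at the redo. The pictures listed in protocol Table 7 document PV isolation, AF termination, sinus rhythm conversion and line validation, not the starting rhythm.

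**The plan's own figures**
- Inputs (protocol 6.2, SAP 4.2.2): 62% and 77% free from AF, one-sided 0.025, 80% power, 146 per arm, 22% drop-out.
- HR = ln(0.77)/ln(0.62) = 0.547, as stated.
- A log-rank calculation with exponential hazards and one year of follow-up gives 80.0% power at 292. The stated size reproduces.
- 292/0.78 = 374.4; the plan states 374.
- Expected events: 146 × 0.38 = 55.5 Anatomical and 146 × 0.23 = 33.6 Tailored, about 89 in total.

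**How many patients could be touched**

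SAP 6.9 says "Given the potential number of patients receiving a second ablation procedure (between 22% and 33" per cent), citing a published trial. 292 × 0.22 = 64 and 292 × 0.33 = 96. This is a ceiling, and a loose one: it includes redos for AT and patients who have already failed on a core-lab recording. The count resting on route 1 alone cannot be derived from the documents.

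**Hypothetical sensitivity of the test**

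Assume no true effect, with 38% events in both arms (55.5 per arm, 111 in total). Let k Tailored events go uncalled and none in the Anatomical arm. The shift in the log-rank statistic is approximately (O₁ − E₁)/√(total/4), with E₁ half of the remaining total.
- k = 3: O₁ = 52.5, total 108, E₁ = 54. Shift = −1.5/√27 = −0.29. One-sided error = Φ(−1.96 + 0.29) = 4.7%.
- k = 5: O₁ = 50.5, total 106, E₁ = 53. Shift = −2.5/√26.5 = −0.49. One-sided error = Φ(−1.96 + 0.49) = 7.0%.
- Mirror case, the same numbers uncalled in the Anatomical arm only: Φ(−1.96 − 0.29) = 1.2% and Φ(−1.96 − 0.49) = 0.7%.

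A second approximation, through the hazard ratio, agrees in scale. A Tailored deficit of 2 percentage points (146 × 0.02 = about 3 patients) gives HR = ln(0.64)/ln(0.62) = 0.934 with 108 events, and an error of Φ(√(108/4) × |ln 0.934| − 1.96) = about 5.4%.

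The values of k are assumptions; nothing in the documents supports any particular one.

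**The case against.** - **The assessor is not stated.** A reader might infer that the operator makes the call. No text says so. The opening words of the core-lab sentence refer to all ECG recordings for these endpoints, which could be stretched to a redo tracing. The full eCRF list and any core-lab charter are not in the documents. This stands: what can be said is that the handling is unspecified and that the listed scope leaves the route out.
- **Asymmetry between arms.** A reader might infer that the spontaneous-or-induced question arises mainly in the Tailored arm. The induction rule in protocol 5.3.4 is not limited to one arm, and the Tailored redo text waives induction for AT recurrences. The Anatomical redo text is silent on induction, so some asymmetry is possible but not established.
- **Direction.** Labelling induced AF as spontaneous would add Tailored events and work against the device. The documents do not fix the direction of any error.
- **Size.** Redos usually follow an observed recurrence. Patients transmit weekly and when symptomatic, and have Holters and ECGs at visits, so many will already have failed on a blinded recording. A patient not called at the redo can still fail later. Deleting k events therefore overstates the loss.
- **Checks already present.** Starting rhythm can be checked, monitors compare CRF entries with source files (protocol 5.6), and the SAP's parenthesis already excludes induced AF. These limit transcription error; they are not blind reading.

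What remains after all this is the coverage gap.

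**Conclusion.** The concern holds as a gap in endpoint adjudication: one of four failure routes is outside the written scope of blinded review, with no named assessor or required tracing. That site staff who know the arm make the call is an inference, though no other assessor is described.

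Its size is unknown. The 64 to 96 redos are only a ceiling. The 4.7% and 7.0% figures are illustrations that assume no true effect, 38% events per arm, losses in the Tailored arm only, and no later failure in those patients. They should not be read as the trial's false-positive rate; equal losses in the other arm would lower it. What they show is that a handful of one-sided calls is enough to matter.

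The sample size is unaffected. The change is worth making because it is cheap and closes the one route without written blinded review.

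**What to change.** - In SAP 5 item 1, SAP 6.6 and protocol 5.1.2, add a surface-ECG tracing from the start of each redo, taken before any pacing or induction. It goes to the existing core lab with arm identifiers removed and is read blind.
- For redos already done, use archived tracings where they exist.
- If a tracing is missing or unreadable, keep site-recorded AF as a failure in the primary analysis. Counting item 1 only when the core lab reads AF would drop true failures, and unevenly if retrieval differs by arm. That is possible, because protocol Table 1 allows any EP recording system in the Anatomical arm but only two named systems in the Tailored arm.
- Report primary failures by route and by arm.
- Add a sensitivity analysis of the primary endpoint that counts only core-lab-read events.

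The cost is a short amendment, one extra upload and one extra reading per redo, and two added outputs. Some past tracings may not be retrievable. Patient treatment does not change.

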6.1 INTERIM ANALYSIS

This trial will employ an adaptive design for the blinded re-estimation of the sample size. To ensure the study is adequately powered for the superiority comparison for the primary outcome measure, the assumptions regarding the rates of AF in both study arms will be verified after 50% of the originally planned total patient sample have complete primary endpoint information. A conditional power (CP) approach for sample-size re-estimation using the Mehta-Pocock approach will be utilized. Following this interim assessment, the sample size may only remain the same or be increased. A third-party, independent statistician will perform this analysis to minimize operational bias. This analysis will occur after approximately 50% of the originally planned subjects a completed/analyzable primary endpoint. The statistician will assess the conditional study power assuming that the hazard ratio remains the value estimated at this analysis. The conditional power will be categorized into one of the three following zones:

Favorable: CP ≥ 80%

Promising: 36% ≤ CP < 80% Unfavorable: CP < 36%

The lower bound on the promising results is selected from Mehta and Pocock as a function of the target power, timing of the sample size re-estimation, and maximum sample size. Selection of this boundary in particular does not inflate the overall Type I error rate. After the analysis, the statistician will provide a recommendation to the Steering Committee and Volta Medical clinical team:

- In the event that the conditional power is found to be in the Unfavorable zone, the study will continue to the originally planned sample. The independent statistician will report ONLY that the trial will continue as originally planned.
- In the event that the conditional power assessment is Promising, the sample size will be increased to 100 total subjects (an additional 50 maximum per treatment arm, predetermined by Volta). The independent statistician will report that the sample size should be increased and by how many subjects (in regard to the 292 subjects originally planned).
- In the event that the conditional power is found to be in the Favorable zone, the study will continue to the originally planned sample. The independent statistician will report ONLY that the trial will continue as originally planned.

Also, the following information will be shared with senior, non-operational management staff that have a strict business need to review and act on the results:

- The recommendation (sample size increase or continue as originally planned)
- The rate of freedom from AF for each arm for the overall interim analysis population
- The rate of freedom from AF for each arm for two subgroups depending on the AF type (persistent AF and long-standing persistent AF)

None of the clinical operational staff or study investigators will have access to the interim data on which the analysis is based to further minimize operational bias. The scientific soundness of the study is not likely to be impacted as the only potential change to the study as a result of this analysis is an increase in sample size.

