## 6.3 – Degree of significance and power of the clinical investigation

Assumptions for the superiority endpoint include a one-sided 0.025 alpha level and 80% power.

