4.2.2 Sample Size

The primary endpoint is freedom from AF, 12 months after a single ablation procedure. Assuming that 62% of the Subjects in the anatomic group will be free from AF at the end of follow-up1,2, that at least 77% of the Subjects of the tailored group will be free from AF at the end of follow-up (i.e., Hazard Ratio (HR) 0.547), then 292 Subjects (146 in each group) are required to show that time to AF is significantly different between groups (Log-Rank test for a one-sided superiority trial, significance level α =0.025, statistical power of 80%, under the assumption that the hazard rates are proportional). Assuming a drop-out rate of 22% (no index ablation performed or loss to follow up), 374 Subjects are required overall (187 in each group). Following 50% of subjects having a primary endpoint collected, the sample size will be re-estimated using the Mehta-Pocock conditional power (CP) approach.

4.2.3 **Primary Analysis**

The primary endpoint will be analyzed using a Cox Proportional hazards model to conduct a time-to-event comparison (of hazard rates from risk of AF recurrence at a time t) between the Tailored (treatment) and Anatomical (control) groups. The model will include an indicator for group (study arm), a dichotomous effect for AF duration (persistent AF \geq 6 months; persistent AF \leq 6 months), and applying right-censoring of subjects lost to follow-up. The model will be used to estimate the hazard ratio of AF occurrence between the Tailored arm compared to that of the Anatomical arm, along with a two-sided 95% CI and p-value for the HR on behalf of the group predictor. The actual null hypothesis of the Primary Endpoint will

be tested with a one-sided Log-Rank test at a significance level of α =0.025. The null hypothesis will be rejected if the p-value is < 0.025, and the survival distribution of the Tailored arm will be considered superior relative to that of the Anatomical arm. All of the outputs described above will be generated under the same single Cox Proportional hazards model, which will be conducted in the mITT population. A Kaplan-Meir plot will be generated to visually display the survival distributions of the Tailored and Anatomical arms, respectively to accommodate the p-value from their comparison.

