6.5 RANDOMIZATION

After successful enrollment, the patient will be automatically randomized in a 1:1 ratio to one of two arms through the eCRF system: "Anatomical" arm (PVI) or "Tailored" arm (Dispersion + smart-PVI). Randomization will be stratified in order to balance the treatment arms in terms of subjects with persistent AF (< 12 months) and long-standing persistent AF (≥ 12 months). Subjects will not be informed of their randomization assignment.

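### SAP 6.1 misstates the promising-zone increase, leaves its base and final size open, and gives a 36% bound that does not follow from adding 100 subjects

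*SAP*

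**What the plan says.** SAP 6.1 defines three zones of conditional power, computed at the hazard ratio seen at the interim: favourable (80% or more), promising (36% up to 80%) and unfavourable (below 36%). The sample size may stay as planned or grow. In the promising zone "the sample size will be increased to 100 total subjects (an additional 50 maximum per treatment arm, predetermined by Volta"). The independent statistician then reports that the size should rise and "by how many subjects (in regard to the 292 subjects originally planned").

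SAP 4.2.2 gives 292 as the number needed for 80% power and, after a 22% drop-out allowance, "374 Subjects are required overall (187 in each group"). Protocol 5.2.6 and 6.2 also give 374 as the number to include.

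SAP 6.1 says that the lower bound of the promising zone was taken from the cited promising-zone method as a function of target power, interim timing and maximum sample size, and adds: "Selection of this boundary in particular does not inflate the overall Type I error rate". No maximum total is stated. The interim takes place when about half of the planned subjects have primary endpoint data. Freedom-from-AF rates by arm then go to senior management outside trial operations.

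Protocol 6.6 leaves the details to the SAP, and SAP 3 makes the SAP prevail, so no other text settles the rule.

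**The concern.** This is the trial's only adaptation, and the number of added subjects is what the statistician must report. Three things look wrong.

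- The stated new total of 100 is smaller than 292 and 374, so the literal instruction contradicts the rule against a decrease.
- Reading *to* as *by* still leaves the base open. The text calls 292 the planned number, but 374 is the enrolment target, and nothing says whether the extra 100 are evaluable or enrolled subjects.
- A bound that depends on the maximum sample size should change with that maximum. A bound of 36% looks low for an increase of about a quarter to a third.

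An adaptive rule is credible because it is fixed before interim data are seen. Here the final size could be settled after arm-level results have reached the sponsor's management.

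**Working it through.** **Inputs.** Freedom from AF 62% versus 77% (SAP 4.2.2), one-sided alpha 0.025 and 80% power (Protocol 6.3), 1:1 allocation (SAP 6.5), 22% drop-out, 292 and 374 subjects (SAP 4.2.2), zone 36% to 80%, interim at about 50% (SAP 6.1).

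**The plan's own sizes reproduce.** HR = ln 0.77 / ln 0.62 = 0.547. A Lakatos-type log-rank calculation with exponential survival gives power 0.800 at 292. Drop-out: 292 / 0.78 = 374.4, and 374 × 0.78 = 291.7. So 292 is the evaluable number and 374 the enrolled number.

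**What an increase of 100 could mean.**
- Evaluable base: 292 + 100 = 392 evaluable, 392 / 0.78 ≈ 503 enrolled. Ratio to plan 392 / 292 = 1.342.
- Enrolled base: 374 + 100 = 474 enrolled, 474 × 0.78 ≈ 370 evaluable. Ratio 474 × 0.78 / 292 = 1.266.
- Trigger: 0.5 × 292 = 146, or 0.5 × 374 = 187.

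**The 36% bound.** Let t be the information fraction at the interim, z the interim statistic, and r the final information relative to plan (r = 1 means no increase). The final test is unadjusted at 1.96.

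- Conditional error under the null: CE(z, r) = 1 − Φ[(1.96√r − z√t) / √(r − t)]
- Conditional power at the current trend: CP(z, r) = 1 − Φ[(1.96√r − z√t) / √(r − t) − z√(r − t) / √t]

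The no-inflation bound is the CP at r = 1, taken at the z where CE(z, r) = CE(z, 1). With t = 0.5:

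| Maximum | r | z at bound | Bound on CP |
|---|---|---|---|
| Doubled sample | 2.000 | 1.203 | 35.8% |
| 292 to 392 evaluable | 1.342 | 1.296 | 42.9% |
| 374 to 474 enrolled | 1.266 | 1.312 | 44.2% |

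Only the doubled sample rounds to 36%; exactly 36% needs r = 1.97. Other readings of the timing do not help. At t = 187/292 = 0.64, 36% needs r of about 1.81, while 392/292 gives 42.0%. At t = 146/374 = 0.39, 36% needs r of about 2.09, while 474/374 gives 44.6%.

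**At the lower edge of the stated zone.** For t = 0.5 and r = 1, CP = 1 − Φ(2.772 − 2z), so CP = 36% at z = 1.207.
- Conditional error without an increase: 0.0588. With r = 1.342 or 1.266: 0.0612.
- Conditional power rises from 36% to 51% (r = 1.342) or 48% (r = 1.266). A doubled sample would give 70%.

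**Overall type I error.** Integrating CE over the null distribution of z, with the full increase applied whenever CP is from 36% to 80%, gives 0.0244 (r = 1.342) and 0.0245 (r = 1.266). If the increase is a cap, taken only as far as needed to reach 80% CP, the values are 0.0246 and 0.0247. The excess between 36% and the recomputed bound is about 0.00002, and the rest of the zone more than offsets it.

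**The case against.** The strongest reply is that the rule can be used. The parenthesis in the same sentence allows up to 50 more per arm, the statistician is asked for an increment, and the zones and the conditional power assumption are explicit. That stands: a reader might infer that the adaptation cannot be carried out, but the text supports a workable reading and a mismatched bound does not prevent execution.

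A reader might also take the 292 base to mean a new enrolment total of 392, only 18 above 374, so that a promising result adds almost nothing. That reading would give 392 × 0.78 ≈ 306 evaluable and lift conditional power from 36% to only 38%. It is the weakest one. SAP 4.2.2 defines 292 before drop-out, and the interim is timed by subjects with an analysable endpoint, so 292 is used as an evaluable count throughout. The real ambiguity is between 392 evaluable and 474 enrolled.

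Finally, a reader might infer that the 36% bound inflates the type I error. The documents do not support this. The SAP claims no overall inflation, and the calculation agrees, even for 392 enrolled (0.0249). Only the pointwise condition behind the bound fails, between 36% and about 43% to 44%.

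The reply does not remove the literal contradiction, the missing base and maximum, or the mismatch between the bound and its stated derivation.

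**Conclusion.** The point holds as an error in the stated size and in the stated basis of a threshold. The figure of 100 total subjects is wrong on any base. The final size is open between 392 evaluable (about 503 enrolled) and 474 enrolled (about 370 evaluable), a difference of about 29 in enrolment and 22 in evaluable subjects. The trigger is open between 146 and 187. The 36% bound belongs to a sample about twice the plan, whereas an increase of 100 corresponds to 42.9% or 44.2%.

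Overall one-sided alpha stays at about 0.0244 to 0.0249, so the SAP's sentence on type I error is true and the inference is not damaged.

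These results assume normal-theory conditional power at the current trend, information proportional to evaluable subjects, an interim at half the information, and an unadjusted final test at 1.96. The documents do not settle which base was intended, so neither 474 enrolled nor a 44% bound can be called the right one from the text.

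**What to change.** In SAP 6.1:

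1. Replace the phrase giving 100 total subjects with *by up to 100 subjects (50 per arm)*.
2. State whether the base is evaluable (292 to 392) or enrolled (374 to 474), give the resulting maximum number, and say whether the increase is fixed or a cap.
3. Use the same base for the 50% trigger, given as a number of subjects, and for the statistician's report.
4. For the bound, do one of two things. Keep 36%, remove the statement that it derives from the maximum sample size, and report the computed overall alpha. Or, only if the interim has not yet been done, reset it to the value for the chosen maximum: about 43% for 392 evaluable, about 44% for 474 enrolled. The documents do not say whether the interim has taken place; if it has, moving the threshold would be a change of rule after the data were seen.

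Items 1 to 3 and the first option in item 4 cost only wording and a short calculation. Resetting the bound slightly narrows the promising zone.
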